		Severe	xx (xx.x)	xx (xx.x)	xx (xx.x)	xx (xx.x)
PT2.1		Mild	xx (xx.x)	xx (xx.x)	xx (xx.x)	xx (xx.x)
		Moderate	xx (xx.x)	xx (xx.x)	xx (xx.x)	xx (xx.x)
		Severe	xx (xx.x)	xx (xx.x)	xx (xx.x)	xx (xx.x)

ETC.

Adverse events coded using the Medical Dictionary for Regulatory Activities (MedDRA version 19.1 or higher). Sorted by descending total incidence by system organ class and preferred term within system organ class. Subjects experiencing the same TEAE more than once are counted only once at each summary level.

Source: list SAS datasets used to create table
SAS X.Y

DDMONYYYYTHH:MM
program_name

Pacira Pharmaceuticals (Page X of Y) Protocol: 404-C-201
Table 14.3-5.1.7: Tabulation of Incidence of Treatment-Emergent Adverse Events (TEAEs) by Relationship to
Study Drug - Safety Analysis Set

Site: Overall

System Organ Class	Preferred Term	DepoTXA 400		DepoTXA 800		DepoTXA 1200		IV TXA		Total [N=XXX] n (%)
		[N=XX] n (%)								
Subjects with at least one TEAE	Unrelated	xx (xx.x)								
	Unlikely	xx (xx.x)								
	Possible	xx (xx.x)								
	Probable	xx (xx.x)								
	Definite	xx (xx.x)								
	Not Reported	xx (xx.x)								
SOC1	Unrelated									
	Unlikely	xx (xx.x)								
	Possible	xx (xx.x)								
	Probable	xx (xx.x)								
	Definite	xx (xx.x)								
	Not Reported	xx (xx.x)								
PT1.1	Unrelated	xx (xx.x)								
	Unlikely	xx (xx.x)								
	Possible	xx (xx.x)								
	Probable	xx (xx.x)								
	Definite	xx (xx.x)								
	Not Reported	xx (xx.x)								
PT1.2	Unrelated	xx (xx.x)								
	Unlikely	xx (xx.x)								
	Possible	xx (xx.x)								
	Probable	xx (xx.x)								
	Definite	xx (xx.x)								
	Not Reported	xx (xx.x)								
ETC.										

Adverse events coded using the Medical Dictionary for Regulatory Activities (MedDRA version 19.1 or higher). Sorted by descending total incidence by system organ class and preferred term within system organ class. Subjects experiencing the same TEAE more than once are counted only once at each summary level.

Source: list SAS datasets used to create table
SAS X.Y

DDMONYYYYTHH:MM
program_name

Note to programmer: Only present overall sites. Use template 14.3-5.1.2 for the following tables:

Table 14.3-5.2.1: Tabulation of Incidence of Serious Treatment-Emergent Adverse Events (TEAEs) - Safety Analysis Set

Table 14.3-5.2.1.CT: Tabulation of Incidence of Non-Serious Treatment-Emergent Adverse Events (TEAEs) - Safety Analysis Set

Table 14.3-5.2.2: Tabulation of Incidence of Study Drug-Related Serious Treatment-Emergent Adverse Events (TEAEs) - Safety Analysis Set

Table 14.3-5.2.3: Tabulation of Incidence of Serious Treatment-Emergent Adverse Events (TEAEs) Leading to Study Withdrawal - Safety Analysis Set

Table 14.3-5.2.4: Tabulation of Incidence of Study Drug-Related Serious Treatment-Emergent Adverse Events (TEAEs) Leading to Study Withdrawal - Safety Analysis Set

Table 14.3-5.2.5: Tabulation of Incidence of Serious Treatment-Emergent Adverse Events (TEAEs) Resulting in Death - Safety Analysis Set

Table 14.3-5.2.6: Tabulation of Incidence of Study Drug-Related Serious Treatment-Emergent Adverse Events (TEAEs) Resulting in Death - Safety Analysis Set

Table 14.3-5.3.1: Tabulation of Incidence of Treatment-Emergent Adverse Events (TEAEs) of Special Interest - Safety Analysis Set

Table 14.3-5.3.2: Tabulation of Incidence of Study Drug-Related Treatment-Emergent Adverse Events (TEAEs) of Special Interest - Safety Analysis Set

Table 14.3-5.3.3: Tabulation of Incidence of Treatment-Emergent Adverse Events (TEAEs) of Special Interest Leading to Study Withdrawal - Safety Analysis Set

Table 14.3-5.3.4: Tabulation of Incidence of Study Drug-Related Treatment-Emergent Adverse Events (TEAEs) of Special Interest Leading to Study Withdrawal - Safety Analysis Set

Table 14.3-5.3.5: Tabulation of Incidence of Treatment-Emergent Adverse Events (TEAEs) of Special Interest Resulting in Death - Safety Analysis Set

Table 14.3-5.3.6: Tabulation of Incidence of Study Drug-Related Treatment-Emergent Adverse Events (TEAEs) of Special Interest Resulting in Death - Safety Analysis Set

Pacira Pharmaceuticals		(Page X of Y)		Protocol: 404-C-201					
Table 14.3-6.1: Tabulation of Incidence of Prior Medications - Safety Analysis Set									
Site: Overall									
System Organ Class	Preferred Term	DepoTXA 400 [N=XX] n (%)	DepoTXA 800 [N=XX] n (%)	DepoTXA 1200 [N=XX] n (%)	IV TXA [N=XX] n (%)				
Subjects taking at least one medication		xx (xx.x)	xx (xx.x)	xx (xx.x)	xx (xx.x)				
ATC1		xx (xx.x)	xx (xx.x)	xx (xx.x)	xx (xx.x)				
PN1.1		xx (xx.x)	xx (xx.x)	xx (xx.x)	xx (xx.x)				
PN1.2		xx (xx.x)	xx (xx.x)	xx (xx.x)	xx (xx.x)				
ATC2		xx (xx.x)	xx (xx.x)	xx (xx.x)	xx (xx.x)				
PN2.1		xx (xx.x)	xx (xx.x)	xx (xx.x)	xx (xx.x)				
PN2.2		xx (xx.x)	xx (xx.x)	xx (xx.x)	xx (xx.x)				

ETC.

Medications are coded using World Health Organization Drug Dictionary Enhanced (WHO-DD) September 2016.

Sorted by descending total incidence by ATC and preferred name within ATC.

Prior medications are those stopped before end of surgery.

Subjects using the same prior medication more than once are counted only once at each summary level.

Source: list SAS datasets used to create table
SAS X.Y

DDMONYYYYTHH:MM
program_name

Note to programmer: Only present overall sites. Use this template for the following tables:

Table 14.3-6.2: Tabulation of Incidence of Concomitant Medications - Safety Analysis Set.

On these tables change the footnote 'Prior medications are those stopped before end of surgery' to read 'Concomitant medications are those taken between the end of surgery and discharge from study' on Table 14.3-6.2.

Pacira Pharmaceuticals (Page X of Y) Protocol: 404-C-201
Table 14.3-7: Tabulation of Incidence of Reoperations Due to Hematoma or Wound Dehiscence - Safety Analysis Set

Site: Overall

	DepoTXA [N=XX] n (%)	DepoTXA [N=XX] n (%)	1200 [N=XX] n (%)	IV TXA [N=XX] n (%)	Total [N=XX] n (%)
--	----------------------------	----------------------------	-------------------------	---------------------------	--------------------------

Did the Subject have a Reoperation due to
a Hematoma or Wound Dehiscence?

Yes	xx (xx.x)				
No	xx (xx.x)				

Number of subjects treated with the respective treatment is used as denominator for the respective percentages.

Source: list SAS datasets used to create table
SAS X.Y

DDMONYYYYTHH:MM
program_name

Pacira Pharmaceuticals (Page X of Y) Protocol: 404-C-201
Table 14.4-1a: Summary of Pharmacokinetic Parameters (for Subjects Enrolled Prior to Protocol Amendment 2)
- PK Analysis Set
Site: Overall

PK Parameter	Statistic	DepoTXA 400 [N=XX]	DepoTXA 800 [N=XX]	DepoTXA 1200 [N=XX]	IV TXA [N=XX]
AUC(0-infinity) (hr*ng/mL)	n	xx	xx	xx	xx
	Mean	xx.x	xx.x	xx.x	xx.x
	SD	x.xx	x.xx	x.xx	x.xx
	Minimum	xx	xx	xx	xx
	Median	xx.x	xx.x	xx.x	xx.x
	Maximum	xx	xx	xx	xx
AUC(0-last) (hr*ng/mL)	n	xx	xx	xx	xx
	Mean	xx.x	xx.x	xx.x	xx.x
	SD	x.xx	x.xx	x.xx	x.xx
	Minimum	xx	xx	xx	xx
	Median	xx.x	xx.x	xx.x	xx.x
	Maximum	xx	xx	xx	xx
Etc.	n	xx	xx	xx	xx
	Mean	xx.x	xx.x	xx.x	xx.x
	SD	x.xx	x.xx	x.xx	x.xx
	Minimum	xx	xx	xx	xx
	Median	xx.x	xx.x	xx.x	xx.x
	Maximum	xx	xx	xx	xx

Source: list SAS datasets used to create table
SAS X.Y

DDMONYYYYTHH:MM
program_name

Note to programmer: Pharmacokinetic parameters to appear on this table are, in order of appearance, AUC(0-infinity) (hr*ng/mL), AUC(0-last) (hr*ng/mL), Global Cmax (ng/mL), Global Tmax (hr), Early Cmax (ng/mL), Early Tmax (hr), Late Cmax (ng/mL), Late Tmax (ng/mL), half-life (hr), Lambda_z (/hr).

Table 14.4-1b: Summary of Pharmacokinetic Parameters (for Subjects Enrolled After Protocol Amendment 2) - PK Analysis Set

Pacira Pharmaceuticals (Page X of Y) Protocol: 404-C-201
Table 14.4-2a: Summary of DepoTXA (ng/mL) Over Time (for Subjects Enrolled Prior to Protocol Amendment 2) - PK Analysis Set

Site: Overall		DepoTXA 400 [N=XX]	DepoTXA 800 [N=XX]	DepoTXA 1200 [N=XX]	IV TXA [N=XX]
Time	Statistic				
5 min	n	XX	XX	XX	XX
	Mean	XX.X	XX.X	XX.X	XX.X
	SD	X.XX	X.XX	X.XX	X.XX
	Minimum	XX	XX	XX	XX
	Median	XX.X	XX.X	XX.X	XX.X
	Maximum	XX	XX	XX	XX
15 min	n	XX	XX	XX	XX
	Mean	XX.X	XX.X	XX.X	XX.X
	SD	X.XX	X.XX	X.XX	X.XX
	Minimum	XX	XX	XX	XX
	Median	XX.X	XX.X	XX.X	XX.X
	Maximum	XX	XX	XX	XX
Ect.	n	XX	XX	XX	XX
	Mean	XX.X	XX.X	XX.X	XX.X
	SD	X.XX	X.XX	X.XX	X.XX
	Minimum	XX	XX	XX	XX
	Median	XX.X	XX.X	XX.X	XX.X
	Maximum	XX	XX	XX	XX

Source: list SAS datasets used to create table
SAS X.Y

DDMONYYYYTHH:MM
program_name

Note to programmer: Timepoints to appear on this table are, in order of appearance, For all subjects: at 5, 15, and 30 minutes; and at 1, 2, 4, 6, 8, 12, 16, and 24 hours after study drug administration for all treatment groups and for DepoTXA-treated subjects only: additional timepoints at 36, 48, 60, 72, and 96 hours after study drug administration.

Table 14.4-2a: Summary of DepoTXA (ng/mL) Over Time (for Subjects Enrolled After Protocol Amendment 2) - PK Analysis Set

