7. DEFINITIONS

Study Day

Study Day 1 is defined as the day of surgery. Study day is calculated as the date of event minus the date of surgery plus one (1), if the date of event is on or after the date of surgery. Study day is based on the calendar dates, thus days before the date of study drug administration have negative values while those on or after the date of surgery have positive values.

Treatment-emergent Adverse Events

A TEAE will be any adverse event or pre-existing medical condition that worsens in intensity after the start of study drug and within 30 days of the last dose.

Time 0 (zero)

Time 0 is defined as the date and time of the start of study drug administration.

Time Periods

All schedule times have a window associated with them (see Time and Events Schedule in the Protocol for individual timepoint windows). Various time frames that are dependent on these windows are used in the data analyses. Table 1 defines the actual elapsed times with allowance for the windows that can be included in the window.

Table 1: Time Periods

Defined time frame	Acceptable elapsed times
5 min	3-7 min
15 min	12-18 min
30 min	25-35 min
1h	50-70 min
2h	105-135 min
4h	225-255 min
6h	345-375 min
8h	450-510 min
12h	690-750 min
16h	15-17h
24h	23-25h
36h	34-38h
48h	46-50h
60h	57-63h
72h	68-76h
96h	90-102h
120h	114-126h
Study Day 7	Study Day 6-8
Study Day 14	Study Day 13-15
Study Day 30 Call	Study Day 27-33
Study Day 60 Call	Study Day 57-63

If there are two or more data points that fit the time window the data point that occurs the closest, in absolute value, to the scheduled observation will be used.

Baseline

Baseline is defined as the last available measurement or assessment prior to the start of study drug administration.

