9.8.8. Surgical Wound Aspect Score (SWAS)

The SWAS will be tabulated by treatment group for the efficacy analysis population with number and percentage of subjects for the score of wound oozing, erythema, ecchymosis, and blisters for postsurgical day 2 (study day 3) and study day 7. In addition, the sum of the wound oozing, erythema, ecchymosis, and blister scores will also be tabulated by treatment group for the efficacy analysis population for postsurgical day 2 (study day 3) and study day 7. Percentages will be based on the number of subjects in the treatment group within the efficacy population.

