Abbreviations: AE = adverse event; d = day; D = day; ECG = electrocardiogram; h = hours; ICF = informed consent form; max = maximum; min = minutes; OR = operating room; PACU = post-anesthesia care unit; PK = pharmacokinetic; Preop = preoperative; TUG = timed up-and-go; WOCBP = women of childbearing potential.

* Postsurgical assessments will be conducted at the timepoints specified after the beginning of study drug administration.

¹ The screening visit must take place at least 1 day prior to surgery.

² Also conduct clinical laboratory tests if a patient experiences an AE of special interest or a serious AE (SAE), if appropriate; see footnote 10.

³ Also conduct a neurological assessment if a patient experiences an AE of special interest or an SAE, if appropriate; see footnote 10.

⁴ Postsurgical 12-lead ECGs will be performed at 1 hour (± 15 minutes) and 12 (± 2) hours after study drug administration

⁵ Vital signs will be measured after the patient has rested in a supine position for at least 5 minutes. Also measure vital signs if a patient experiences an AE of special interest or an SAE, if appropriate; see footnote 10.

⁶ Collect knee and thigh measurements (both legs) on the morning of postsurgical Day 2.

⁷ The surgical wound will be assessed for the SWAS parameters (wound oozing, erythema, ecchymosis, and blisters) at the time of knee measurements on the morning of postsurgical Day 2 and on Day 7.

⁸ Also collect a PK sample if a patient experiences an AE of special interest or an SAE; see footnote 10.

⁹ Record date and time of all medications starting at least 30 days prior to study drug administration through 120 hours after study drug administration. Record medications administered for treatment of an AE through Day 60 (± 3 days).

¹⁰ Adverse events of special interest include changes in color vision, VTE or PE, and oliguria. If an AE of special interest or serious AE (SAE) occurs during the study, an unscheduled PK blood sample must be collected. In addition, vital signs, the neurological assessment, and clinical laboratory tests should be conducted, as appropriate. If a patient experiences changes in color vision, an ophthalmological consultation must be ordered.

¹¹ Postsurgical “Timed Up-and-Go” will be assessed once on the day of the surgery; at approximately 8:00 am and 8:00 pm (± 2 hours) daily from Day 2 through hospital discharge; and on Day 7.

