Number of subjects ambulating	n (%)	xx (xx.x)	xx (xx.x)	xx (xx.x)	xx (xx.x)
Number of subjects censored	n (%)	xx (xx.x)	xx (xx.x)	xx (xx.x)	xx (xx.x)
KM Estimates of Days to First Independent Ambulation	n	xx	xx	xx	xx
	Minimum	xx.x	xx.x	xx.x	xx.x
	25 th Percentile	xx.x	xx.x	xx.x	xx.x
	Median	xx.x	xx.x	xx.x	xx.x
	75 th Percentile	xx.x	xx.x	xx.x	xx.x
	Maximum	xx.x	xx.x	xx.x	xx.x

Note: + indicates a censored value; KM = Kaplan-Meier

Source: list SAS datasets used to create table
SAS X.Y

DDMONYYYYTHH:MM
program_name

Pacira Pharmaceuticals (Page X of Y) Protocol: 404-C-201
Table 14.2-8: Tabulation of Surgical Wound Aspect Score on Postsurgical Day - Efficacy Analysis Set
Site: Overall

Study Day	2	DepoTXA			
		400 [N=XX]	DepoTXA 800 [N=XX]	DepoTXA 1200 [N=XX]	IV TXA [N=XX]
		n (%)	n (%)	n (%)	n (%)
Wound Oozing					
	0: No signs of blood on the gauze	xx (xx.x)	xx (xx.x)	xx (xx.x)	xx (xx.x)
	1: 1-2 spots of blood on the gauze	xx (xx.x)	xx (xx.x)	xx (xx.x)	xx (xx.x)
	2: >2 spots of blood on the gauze	xx (xx.x)	xx (xx.x)	xx (xx.x)	xx (xx.x)
Erythema					
	0: Erythema absent	xx (xx.x)	xx (xx.x)	xx (xx.x)	xx (xx.x)
	1: Erythema at wound edges	xx (xx.x)	xx (xx.x)	xx (xx.x)	xx (xx.x)
	2: Erythema beyond wound edges	xx (xx.x)	xx (xx.x)	xx (xx.x)	xx (xx.x)
Ecchymosis					
	0: Ecchymosis absent	xx (xx.x)	xx (xx.x)	xx (xx.x)	xx (xx.x)
	1: Ecchymosis at wound edges	xx (xx.x)	xx (xx.x)	xx (xx.x)	xx (xx.x)
	2: Ecchymosis beyond wound edges	xx (xx.x)	xx (xx.x)	xx (xx.x)	xx (xx.x)
Blisters					
	0: Blisters absent	xx (xx.x)	xx (xx.x)	xx (xx.x)	xx (xx.x)
	1: 1-2 blisters of <2 cm each	xx (xx.x)	xx (xx.x)	xx (xx.x)	xx (xx.x)
	2: >2 blisters of any size or ≥1 blister >2 cm	xx (xx.x)	xx (xx.x)	xx (xx.x)	xx (xx.x)
Sum of Categories					
	0	xx (xx.x)	xx (xx.x)	xx (xx.x)	xx (xx.x)
	1	xx (xx.x)	xx (xx.x)	xx (xx.x)	xx (xx.x)
	2	xx (xx.x)	xx (xx.x)	xx (xx.x)	xx (xx.x)
	3	xx (xx.x)	xx (xx.x)	xx (xx.x)	xx (xx.x)
	4	xx (xx.x)	xx (xx.x)	xx (xx.x)	xx (xx.x)
	5	xx (xx.x)	xx (xx.x)	xx (xx.x)	xx (xx.x)
	6	xx (xx.x)	xx (xx.x)	xx (xx.x)	xx (xx.x)
	7	xx (xx.x)	xx (xx.x)	xx (xx.x)	xx (xx.x)
	8	xx (xx.x)	xx (xx.x)	xx (xx.x)	xx (xx.x)

Descriptive Statistics of the Sum of Categories

n	xx	xx	xx	xx
Mean	xx.x	xx.x	xx.x	xx.x
SD	x.xx	x.xx	x.xx	x.xx
Minimum	xx	xx	xx	xx
Median	xx.x	xx.x	xx.x	xx.x
Maximum	xx	xx	xx	xx

Number of subjects randomized is used as denominator for all percentages.

Source: list SAS datasets used to create table
SAS X.Y

DDMONYYYYTHH:MM
program_name

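### The SWAS table shell (Table 14.2-8) contradicts Section 9.8.8 on the percentage denominator and on the study day of the first assessment

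*SAP*

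**What the plan says.** **Denominator.** For SWAS, SAP Section 9.8.8 states: "Percentages will be based on the number of subjects in the treatment group within the efficacy population". Section 9.1 sets the same default for all tables: unless noted otherwise, percentages use the treatment-group count within the analysis population. Table 14.2-8 is titled as an efficacy-analysis-set table, but its footnote reads "Number of subjects randomized is used as denominator for all percentages". Section 8 restricts the efficacy set to subjects who both received study drug and had the planned surgery.

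**Day.** Section 9.8.8 tabulates SWAS "for postsurgical day 2 (study day 3) and study day 7". Section 7 fixes the count: "Study Day 1 is defined as the day of surgery". The SWAS footnote to the schedule in Section 12 has the wound assessed "at the time of knee measurements on the morning of postsurgical Day 2 and on Day 7". The first page of the Table 14.2-8 shell is headed Study Day 2, and the programmer's note puts study day 7 on the next page.

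**Blister item.** The shell prints score 1 as "1: 1-2 blisters of <2 cm each" and score 2 as "2: >2 blisters of any size or ≥1 blister >2 cm".

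**The concern.** A table shell is the instruction that a programmer follows. Here it disagrees with the method text on the denominator of every SWAS percentage and on the day that the first page describes. If the shell is followed, the percentages may not be those that Section 9.8.8 promises. A table labelled as efficacy set could also divide by subjects outside that set. The first page would name a day on which the plan schedules no wound assessment. SWAS is one of the listed efficacy endpoints for a locally administered product, so its table should be unambiguous, even though nothing is tested on it.

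**Working it through.** The plan gives no numerical result to reproduce for this table, so the check compares sections and adds simple arithmetic.

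**1. Day**

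- Section 7: study day = date of event − date of surgery + 1, for dates on or after surgery. Surgery is study day 1, that is, postsurgical day 0.
- Hence postsurgical day *k* is study day *k* + 1. Postsurgical day 1 is study day 2, and postsurgical day 2 is study day 3.
- Section 9.8.8 gives the same conversion. The Section 12 footnote agrees on postsurgical Day 2, and Listing 16.2-6.7 labels the visit 48h, which fits study day 3.
- The shell's Study Day 2 is therefore postsurgical day 1. SWAS is scheduled only on postsurgical day 2 and Day 7.
- Study Day 2 is hard to excuse as shorthand for postsurgical day 2. The next page of the same table counts in study days, and Section 9.8.4 uses study day 2 literally for the TUG test, with study day 1 equated to postsurgical day 0. The knee circumference shell (Table 14.2-6.1.1) heads its corresponding timepoint as postsurgical day 2.

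**2. Denominator**

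Inputs: 15 subjects planned per arm (Section 6). The number randomized but outside the efficacy set is not known in advance, so 0 to 3 is assumed. The count of 7 in a category is also an illustration.

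| Assumed exclusions in an arm | Efficacy-set n | 7 subjects, shell footnote | 7 subjects, Section 9.8.8 | Total of all categories under the footnote, everyone in the set scored |
|---|---|---|---|---|
| 0 | 15 | 7/15 = 46.7% | 7/15 = 46.7% | 15/15 = 100.0% |
| 1 | 14 | 7/15 = 46.7% | 7/14 = 50.0% | 14/15 = 93.3% |
| 2 | 13 | 7/15 = 46.7% | 7/13 = 53.8% | 13/15 = 86.7% |
| 3 | 12 | 7/15 = 46.7% | 7/12 = 58.3% | 12/15 = 80.0% |

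For a rarer category, three subjects with one exclusion are 3/15 = 20.0% under the footnote and 3/14 = 21.4% under 9.8.8. With no exclusions the two rules agree exactly.

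**3. Blister labels**

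Checking blister counts and sizes against the printed categories:

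- none: score 0;
- one of 1.9 cm: score 1;
- one of 2.1 cm: score 2;
- more than two of any size: score 2;
- one of exactly 2.0 cm, or two with the larger exactly 2.0 cm: no printed category.

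The gap is confined to that single boundary value with one or two blisters.

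**The case against.** **The intended rules are clear.** The footnote looks like carried-over shell text: the same sentence sits under the NRS pain table (Table 14.2-5.1), whose shell shows no percentages. The title, 9.1 and 9.8.8 all point to the efficacy set, and 9.8.8 states the correct day. This stands as an explanation and limits the harm. It does not remove the contradiction, because the shell still gives a different instruction. Nor can the footnote easily be read as shorthand for analysis by randomized arm. The disposition shell (Table 14.1-1) marks that idea separately, as an as-randomized note, and uses the same denominator phrase to mean all subjects randomized.

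**Stronger readings that a reader might infer, and why the SAP does not support them:**

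- *Data from the wrong visit would be tabulated.* No SWAS is scheduled on study day 2, so there are no scheduled records to pick up by mistake. A literal filter would return an empty page; otherwise the right data would carry a wrong label.
- *Both denominators are wrong because they include subjects never scored.* A full-set denominator is a stated and consistent choice (9.1, 9.8.2, 9.8.8). Percentages among scored subjects carry a missing-data bias of their own. Raising the 20.0% above to 3/10 = 30.0% would need 5 of 15 randomized subjects unscored. Nothing in the SAP supports that, or unequal attendance between arms.
- *The blister gap drops the total score for the worst wounds.* Any blister over 2 cm, or more than two of any size, already scores 2. Listing 16.2-6.7 carries item scores and not sizes, and the SAP does not derive the score from measurements. A boundary case is therefore more likely to be scored inconsistently by assessors than to be left missing.

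**Conclusion.** Two contradictions between the Table 14.2-8 shell and Section 9.8.8 are established: the denominator and the day heading.

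The denominator matters only if at least one randomized subject was not treated or not operated on. With 15 per arm and one assumed exclusion, the shift is 1.4 percentage points at three subjects (21.4 − 20.0) and 3.3 points at seven (50.0 − 46.7), always lower under the footnote. With no exclusions it is nil. The day heading affects whether the page is populated and correctly labelled; it does not change which wound assessments are made.

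The blister boundary is a side observation. The printed labels leave exactly 2 cm unassigned for one or two blisters, but neither the CRF nor the source scale is available to show whether the data are affected.

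Importance is low. Section 9.8 plans no formal hypothesis testing for any efficacy endpoint, so the correction makes the table consistent and readable without altering any inference.

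**What to change.** - Replace the Table 14.2-8 footnote with the denominator of Section 9.8.8: subjects in the treatment group within the efficacy analysis set.
- Head the first page Postsurgical Day 2 (Study Day 3), and keep study day 7 for the second.
- Optional: print the number of subjects scored at each timepoint beside the item percentages. The shell already prints n for the sum score, so this lets a reader see any missed assessments without changing the denominator rule.
- Optional: check the blister labels against the CRF or the source scale, and state which category takes a largest blister of exactly 2 cm. The answer should come from that source and not be chosen in the SAP.

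The cost is an edit to SAP and shell wording. No data collection, analysis set or sample size changes.
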